Lactic acidosis	Porphyria	Shock hypoglycaemic
Tetany		

Musculoskeletal, connective tissue and bone disorders

Aseptic necrosis bone	Fracture pathological	Muscle necrosis
Osteomalacia	Rhabdomyolysis	Systemic lupus erythematosus
Systemic sclerosis		

Nervous system disorders

Amnesia	Anticholinergic syndrome	Aphasia
Cerebral oedema	Chorea	Coma
Convulsions	Demyelination	Encephalitis
Encephalopathy	Epilepsy	Guillain Barré syndrome
Hydrocephalus	Intracranial haemorrhage	Meningitis
Multiple sclerosis	Myasthenia gravis	Myelitis
Neuroleptic malignant syndrome	Opisthotonus	Paralysis
Paresis	Parkinson syndrome	Serotonin syndrome
Stroke	Tunnel vision	

Pregnancy, puerperium and perinatal conditions

Abortion	Eclampsia	Intra-uterine death
----------	-----------	---------------------

Psychiatric disorders

Anorexia nervosa	Delirium	Drug abuse
Drug dependence	Homicidal ideation	Intentional misuse
Self-injurious ideation/attempt	Suicidal ideation/attempt	Suicide completed

Renal and urinary disorders

Blood and lymphatic system disorders

Anuria	Goodpasture's syndrome	Haemolytic uraemic syndrome
Nephritis/nephritic syndrome	Nephrotic syndrome	Oliguria
Renal failure acute	Renal tubular necrosis	Urinary obstruction/retention

Reproductive system and breast disorders

Metrorrhagia/uterine haemorrhage	Priapism
----------------------------------	----------

Respiratory, thoracic and mediastinal disorders

Acute respiratory failure	Adult respiratory distress syndrome	Alveolitis allergic
Asphyxia	Bronchospasm	Laryngeal oedema
Pulmonary fibrosis	Pulmonary haemorrhage	Pulmonary infarction
Pulmonary vasculitis	Respiratory arrest	Status asthmaticus
Pulmonary oedema		

Skin and subcutaneous tissue disorders

Angioneurotic oedema	Erythema nodosum	Pemphigus
Stevens Johnson syndrome	Toxic epidermal necrolysis	Vascular purpura

Vascular disorders

Acute circulatory failure	Embolism	Malignant hypertension
Necrosis ischaemic	Thrombosis	

12.4 APPENDIX IV Clinical Laboratory Tests

All samples will be collected in accordance with acceptable laboratory procedures. The maximum volume of blood at any single visit should remain within the following guidelines.

The following chart outlines the guidelines for blood drawing and the max volume which can be safely drawn per day:

Conversions:

lbs/2.2 = kg

kg X 1.7 = mL

Kilograms	(mLs) Volume which can be safely drawn per day
2.7 – 3.6	4.6 – 6.1
4.1-4.6	7.0-7.8
5.0-6.4	8.5-10.8

The following is a list of lab tests collected for each study participant.

Blood	
Comprehensive Metabolic Panel	Complete Blood Count w/ Differential
Glucose	WBC Count
Calcium	RBC Count
Sodium	Hemoglobin
Potassium	Hematocrit
CO2/Bicarbonate	RBC indices (MCV, MCH, MCHC, RDW)
Chloride	Reticulocyte count
BUN	Platelet count
Creatinine	
Total Protein	
Albumin	
Bilirubin (total and direct)	
ALP	
AST	
ALT

7.1. Primary Outcome Analysis.....	15
7.1.1. Primary analysis	15
7.1.2. Per-protocol analysis of the primary outcome	16
7.1.3. Covariate adjusted analysis of the primary outcome	16

CONFIDENTIAL

7.1.4.	Subgroup analysis of the primary outcome	16
7.2.	Secondary outcome Analysis.....	16
7.2.1.	Analysis of binary outcomes	16
7.2.2.	Analysis of continuous outcomes	17
8.	SAFETY ANALYSES	17
8.1.	Adverse event.....	17
8.2.	Vital Signs.....	17
8.3.	Laboratory Data	17
8.4.	Physical Examination	18
8.5.	Dilution and administration procedure of IV Phenobarbital	18
9.	PHAMACOKINETIC ANALYSIS	18
10.	REFERENCES.....	18

CONFIDENTIAL**ABBREVIATIONS**

Abbreviation	Explanation
AE	Adverse Event
ATC	Anatomical-Therapeutic-Chemical
CI	Confidence interval
cvEEG	Continuous video EEG
GEE	Generalized estimating equation
GLM	Generalised linear model
HIE	Hypoxic-Ischemic Encephalopathy
IQR	Inter quarter range
ITT	Intent-to-treat
IWRS	Interactive web response system
PK	Pharmacokinetic
PP	Per-protocol
RD	Risk difference
RR	Risk ratio or relative risk
SAE	Serious Adverse Event
SAP	Statistical Analysis Plan
SD	Standard deviation
TEAE	Treatment emergence adverse event

CONFIDENTIAL**1. INTRODUCTION**

The purpose of this Statistical Analysis Plan (SAP) is to define the outcome variables, statistical methods, and analysis strategies to address the study objectives of the trial: A Randomized, Double-Blind, Controlled Study to Assess the Efficacy and Safety of Intravenous Phenobarbital in Neonatal Seizures (Protocol Version 2.0 and 07- Dec-2021).

The pharmacokinetic analysis is outside the scope of this analysis plan. That analysis will be described in a separate document. Prior to unlocking of the data base a determination will be made if an exploratory pharmacokinetic analysis will be performed based on the total number of plasma samples available.

2. STUDY OBJECTIVES

This study is designed to evaluate the efficacy, safety and tolerability of intravenous phenobarbital in treatment of neonatal seizures diagnosed by continuous video EEG (cvEEG).

2.1. Primary Objective

To evaluate a potential dose-response of two different doses of intravenous phenobarbital for safety and efficacy in a neonatal population at high risk for seizures.

2.2. Secondary Objectives

- To assess the safety and tolerability of intravenous phenobarbital administration in neonates experiencing seizures.
- To assess the requirement of a second dose of intravenous phenobarbital in neonates with ongoing seizures.
- To assess the requirement of alternative anticonvulsive therapy in neonates with ongoing seizures after the second dose of intravenous phenobarbital.
- To characterize the seizure burden following administration of intravenous phenobarbital.

2.3. Exploratory Objectives

- To characterize the population pharmacokinetics of intravenous phenobarbital in neonates with seizures.
- To evaluate a potential dose-response of two different doses of intravenous phenobarbital for safety and efficacy in neonatal populations with different seizure etiologies.

CONFIDENTIAL

3. STUDY DESIGN

3.1. Design

This is a multicenter, randomized, double-blinded, active-controlled, parallel study in neonates (≥ 34 weeks). The study will consist of a Screening Period, Double-Blind Treatment Period, Follow-up Period and an Open-Label Period. This study will consist of a Screening Period, Treatment Period, Follow-up Period and Open Label Extension Period.

3.2. Treatments

Treatment A: Phenobarbital 20 mg/kg (first/initial dose) followed by 20 mg/kg (if required)

Treatment B: Phenobarbital 40 mg/kg (first/initial dose) followed by 10 mg/kg (if required)

The initial dose will be administered intravenously over a 30-minute period.

3.3. Eligibility

3.3.1. Inclusion Criteria

In order to be eligible to participate in this study, an individual must meet all of the following criteria:

1. Male or female neonates with a gestational age of ≥ 34 - ≤ 44 weeks admitted into the NICU with a high probability of developing seizures (e.g., Hypoxic-Ischemic Encephalopathy (HIE), stroke, intracerebral hemorrhage, central nervous system infection)
2. Parental informed consent
3. Undergoing cvEEG monitoring
4. Has evidence of electrographic seizure burden of at least 30 seconds/h

3.3.2. Exclusion Criteria

An individual who meets any of the following criteria will be excluded from participation in this study:

1. Received anticonvulsant treatment, including phenobarbital, prior to randomization
2. Strong suspicion or confirmed diagnosis of brain malformation, inborn error of metabolism genetic syndrome, or major congenital malformation prior to randomization
3. Seizures responding to correction of hypoglycemia, hypocalcemia or any other metabolic disorder
4. Death appears to be imminent as assessed by the NICU attending physician

3.4. Randomisation

Subjects will be assigned unique subject numbers upon completion of the Screening Period and upon achieving the seizure criteria.

CONFIDENTIAL

A unique randomization number will be assigned by an interactive web response system (IWRS) once eligibility for the Treatment Period of the study has been determined. A permuted block randomization list will be prepared by an external-to-study, unblinded biostatistician.

Detailed instructions for contacting the IWRS will be provided in the Study Manual. The PI or designee will use the IWRS to determine which IMP will be dispensed to a given subject for the Treatment Period of the study. The unblinded investigational pharmacist will prepare the IMP and provide to the PI or designee for administration.

3.5. Unblinding

The Investigator may unblind an individual subject's treatment in an emergency when knowledge of such treatment may have an impact on further treatment decisions or aid in the emergency treatment of the subject. Every effort must be made to contact the Medical Monitor prior to any unblinding of the study drug. The circumstances that lead to unblinding will be promptly communicated via telephone and in writing to the Medical Monitor.

3.6. Sample Size

Literature supports that lower loading doses of phenobarbital achieve seizure control in approximately 30 to 60% of treated neonates, with higher loading doses achieving seizure control up to 85%. Based on an effect size of 20% (from 50% in the low dose group to 70% in the high dose group), an alpha of 0.05 and 80% power, it is estimated that the number of completed subjects required will be 93 subjects in each group (total 186). With approximately, 5% dropout resulting in non-evaluable primary outcome, the minimum required for randomization will be 196.

3.7. Outcomes

3.7.1. Primary outcome

Primary outcome is defined as a binary outcome indicating whether a neonate requires additional seizure treatment after the first dose of phenobarbital during the first 24 hours after treatment (1 for yes and 0 for No), which will be summarized as the percentage of neonates requiring additional seizure treatment.

The primary endpoint is in line with recommendations provided by the US Food and Drug Administration. This measure should provide a clear delineation of the efficacy between the low and high loading doses of intravenous phenobarbital.

3.7.2. Secondary outcomes

Efficacy

- Percent of neonates who do not require additional seizure treatment after 2 hours of the first dose of phenobarbital.

CONFIDENTIAL

- Percent of neonates who do not require additional seizure treatment after the second dose of phenobarbital within the first 24 hours of treatment.
- Seizure burden over 24 hours following initial administration of the phenobarbital injection.
- Seizure burden over 48 hours following initial administration of the phenobarbital injection.
- Percent of neonates requiring alternative anticonvulsive therapy for the management of seizures at 24 and 48 hours.
- Time period between the first dose and second dose of intravenous phenobarbital in neonates randomized.
- Time period between the second dose of intravenous phenobarbital and alternative anticonvulsant treatment in neonates
- Time period between the first dose of intravenous phenobarbital and administration of an alternative anticonvulsant treatment in neonates randomized.

Safety

The following safety assessments will be performed during the study:

- Type, incidence, and severity of adverse events
- Physical examination
- Vital signs (blood pressure [arterial line], respiration rate, pulse rate, oxygen saturation and temperature)
- Clinical laboratory tests (hematology, serum chemistry)

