If seizures persist (≥ 30 sec/h of seizure activity) 60 minutes following the start of the initial dose of phenobarbital, neonates receiving an initial dose of 20 mg/kg will receive an additional 20 mg/kg dose. Neonates receiving an initial dose of 40 mg/kg will receive an additional 10 mg/kg dose. Administration of this second loading dose is required to be within 2 hours of recognition of qualifying seizure burden (≥ 30 sec/h). The time period between the first and second dose of study treatment will be determined by the principal investigator or site designee (recommended to be a pediatric neurologist and/or neurophysiologist) review of the cvEEG, but must be at least 30 minutes after infusion is completed and no more than 24 hours after the first dose of study treatment (22).

If the seizure activity continues (≥ 30 sec/h) is still not resolved, study participants may receive a second-line alternative anticonvulsant therapy per institutional protocol. In each treatment arm, the second-line anticonvulsant therapy will be confirmed by the principal investigator or site designee (recommended to be a pediatric neurologist and/or neurophysiologist) and recorded in the study documentation as a concomitant medication.

All phenobarbital treatment doses will be prepared by the unblinded investigational pharmacist. The investigational pharmacist will be unblinded (have access to the treatment arm labels) and will not be involved in the assessment or medical management of the neonate. All other study personnel will be blinded to the first and second phenobarbital dose treatment. Each study treatment arm will be prepared in the same total volume of administration and administered over a **30-minute infusion** in order to maintain the study blind.

Throughout the Treatment Period the neonate will be continuously monitored by cvEEG, vital signs will be recorded, clinical seizure assessment will be recorded, and blood samples will be collected for laboratory safety monitoring and phenobarbital plasma concentrations according to the schedule of activities (Section 1.3). cvEEG monitoring will continue throughout the Treatment

Period and will be discontinued at end of Follow-up Period or upon entering Open Label Extension Period.

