A population pharmacokinetic approach will be implemented using sparse sampling collection. Collection of plasma samples for phenobarbital analysis will be obtained after each loading dose and will follow the sampling guidelines in the schedule of activities (Section 1.3). Additional plasma samples will be obtained at the completion of the treatment period or at early study discontinuation. In order to maintain the study blind, the phenobarbital plasma concentrations will not be made available to the study personnel.

Seizure management in the treatment period will be determined by cvEEG monitoring. Recording of all vital signs and collection of laboratory safety monitoring and collection of phenobarbital plasma samples will be dependent on the clinical management and status of the neonate. The principal investigator will be allowed to discontinue the neonate from the study protocol at any time throughout the study protocol and allowed to administer alternative anticonvulsant therapy as medically required or following standard of care guidelines.

The study treatment period for the primary study analysis will end 24 hours after the neonate meets the seizure criteria and receives the initial phenobarbital study dose (i.e. T0-24 hr). Prior to completing the Treatment Period or early study discontinuation, cvEEG assessment, clinical seizure assessment, and vital signs will be recorded, clinical laboratory tests will be performed, and a phenobarbital plasma sample will be collected. The neonate will be monitored for an additional 24 hours (Follow-up Period) after the Treatment Period is completed. During the 24-hour Follow-up Period general seizure activity, administration of additional non-study anticonvulsant medication, and adverse events will be recorded. Neonates requiring ongoing/maintenance intravenous phenobarbital therapy following study treatment completion will enter an Open Label Extension Period (up to 3 days) and will be monitored for safety and additional phenobarbital plasma samples will be obtained while they are on therapy and until hospital discharge. All study related assessments and work related to the study will be compensated by the funding Sponsor.

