5.2. Data Summaries

Continuous variables will be summarised according to number of subjects with non-missing data (n), mean, standard deviation (SD), median, minimum, and maximum.

Categorical variables will be summarised according to the absolute frequency and percentage of subjects (%) in each category level. The denominator for the percentages is the number of subjects in the treatment arm with data available, unless noted otherwise.

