7.2. Secondary outcome Analysis

All secondary outcomes will be analyzed as a superiority design and two-sided 95% CIs for the treatment differences in these outcomes between two treatment groups will be calculated and presented. Secondary outcome analyses will be based on the ITT population unless specified.

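### The secondary endpoint on response after the second dose does not say how neonates without a second dose are scored, so its between-arm comparison may be non-randomised or misordered

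*SAP*

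**What the plan says.** SAP 3.7.2 lists two secondary efficacy outcomes that start at the second dose: "Percent of neonates who do not require additional seizure treatment after the second dose of phenobarbital within the first 24 hours of treatment" and "Time period between the second dose of intravenous phenobarbital and alternative anticonvulsant treatment in neonates". Protocol 1.1 and 3.2.2 carry the same endpoints.

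The second dose is conditional. Protocol 4.1 gives the trigger: "If seizures persist (≥ 30 sec/h of seizure activity) 60 minutes following the start of the initial dose of phenobarbital". When it is met, "neonates receiving an initial dose of 20 mg/kg will receive an additional 20 mg/kg dose" and "Neonates receiving an initial dose of 40 mg/kg will receive an additional 10 mg/kg dose". Under the same section the investigator is "allowed to administer alternative anticonvulsant therapy as medically required or following standard of care guidelines", so a neonate who fails the first dose may go to another drug without a second dose.

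For the analysis, SAP 7.2 states: "Secondary outcome analyses will be based on the ITT population unless specified". It frames all secondary outcomes as superiority comparisons with two-sided 95% confidence intervals for the treatment difference. SAP 5.2 adds: "The denominator for the percentages is the number of subjects in the treatment arm with data available, unless noted otherwise". SAP 5.5.3 rules out imputation for outcomes other than the primary; the rule in SAP 5.5.2 that missing responses are failures covers the primary outcome only. SAP 5.6 calls the secondary analyses exploratory.

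SAP 3.7.2, 7.2 and 7.2.1 do not say whether a neonate with no second dose is a success, a failure or excluded.

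**The concern.** Receiving a second dose is a consequence of first-dose failure, which is the event the primary endpoint expects to differ between arms. An outcome that starts at the second dose therefore has no evident value for a large share of the ITT population, and that share is expected to be larger in the high-dose arm. The value assigned to those neonates decides what is estimated. One choice gives a non-randomised comparison, another ranks the arms in the wrong order, and a third gives a sensible randomised comparison. Because SAP 7.2 asks for a between-arm interval, one of these will be computed and reported, and the plan does not say which.

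**Working it through.** **Inputs from the documents.** First-dose control is 50% low and 70% high, alpha 0.05, power 80%, 93 per group completed and 196 randomised (SAP 3.6; Protocol 9.2). Allocation is 1:1 (Protocol 4.1), so 98 per arm.

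**Assumptions.** The documents give no response rate to the second dose. Call it r, equal in both arms unless stated. Every first-dose failure is taken to receive the second dose.

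**The plan's own figure.** With the pooled-variance formula, two-sided, n = [1.960·√(2·0.6·0.4) + 0.842·√(0.5·0.5 + 0.7·0.3)]² / 0.2² = 93 per arm. Then 186/0.95 = 195.8, rounded up to 196. Both figures reproduce.

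**Reading 1: recipients only.** This follows if a neonate without a second dose is treated as having no data (SAP 5.2, 5.5.3).
- Recipients: 98 × 0.50 = 49 low; 98 × 0.30 = 29.4, about 29, high.
- Percentages: r against r. Equal r shows no difference and no reversal. The two groups are nevertheless differently selected, failures of 20 mg/kg against failures of 40 mg/kg, and then receive different second doses, so equal r is not to be expected.
- Illustration only: suppose control depends on cumulative dose, with 50% controlled at 20 mg/kg, 70% at 40 mg/kg and an assumed x at 50 mg/kg. Among recipients, low = (0.70 − 0.50)/0.50 = 40% and high = (x − 0.70)/0.30, which is 17%, 33% or 50% for x = 0.75, 0.80 or 0.85. The high arm looks worse among recipients whenever x is below 0.82, although in all randomised neonates it is better (x against 70%).

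**Readings 2 and 3: all randomised neonates.** Reading 2 counts a success only if a second dose was given and nothing more was needed: low 0.5r, high 0.3r. Reading 3 also counts first-dose responders as successes: low 0.5 + 0.5r, high 0.7 + 0.3r.

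| r (assumed) | Reading 2, low vs high | Reading 3, low vs high |
|---|---|---|
| 0.3 | 15% vs 9% | 65% vs 79% |
| 0.5 | 25% vs 15% | 75% vs 85% |
| 0.7 | 35% vs 21% | 85% vs 91% |

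- Reading 2: high minus low = −0.2r, the wrong sign for every equal r above 0. The order comes right only if the high arm's r exceeds 0.5/0.3 = 1.67 times the low arm's. With 98 per arm and a simple two-sided 0.05 comparison of proportions, the chance of a significant result in the wrong direction is about 18%, 42% and 67% at r = 0.2, 0.5 and 0.8.
- Reading 3: high minus low = 0.2(1 − r), the right sign for every equal r below 1.

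**Time from second dose to alternative drug.** The clock exists only for second-dose recipients, so the selection in reading 1 applies. Protocol 9.4.3 plans Kaplan-Meier and Cox methods for time-to-event outcomes, but SAP 7.2 has sections only for binary and continuous outcomes and gives no censoring rule. The calculation in reading 2 does not carry over to a duration, and no sign reversal is shown for it.

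**The case against.** The best defence is that reading 3 is available on the plain words. A first-dose responder does not need more treatment after a second dose, so on ITT that neonate can count as a success with no added condition. This reading keeps the randomised comparison and orders the arms correctly. That stands: a reader might infer that the endpoint breaks the randomised comparison however it is read, and the documents do not support so broad a statement.

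A reader might also take 25% against 15% as what the plan will produce. It is not the best-supported reading. It adds a requirement to have received a second dose and scores first-dose responders as failures, and no rule for secondary outcomes says so. It also rests on an r that the documents do not give, set equal across arms although the second doses differ.

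Two further points stand. SAP 3.7.2 already lists the percentage needing alternative anticonvulsive therapy at 24 and 48 hours, and the time from first dose to alternative treatment, both definable for all randomised neonates. And SAP 2.2 has an objective about alternative therapy in neonates still seizing after the second dose, so describing recipients is a legitimate aim.

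None of this removes the gap. The existence of a sound reading does not select it, and the SAP's denominator and missing-data rules point towards recipients only.

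**Conclusion.** The point holds as an undefined numerator and denominator with material consequences. As written, the plan most naturally yields a comparison of about 49 against 29 second-dose recipients, which is not randomised. A second coding would misorder the arms by 6, 10 or 14 percentage points at r = 0.3, 0.5 or 0.7 (differences from the table), and a third orders them correctly. The reversal is possible, not inevitable. The recipient counts rest on the planning rates and on every first-dose failure receiving a second dose; the percentages rest also on an assumed, equal r. The second-dose-to-alternative interval shares the selection problem only.

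The impact is confined to secondary endpoints that the SAP calls exploratory, with sound all-neonate endpoints beside them. The primary endpoint, its analysis and the sample size are unaffected. It should still be settled before unblinding, because the choice of coding could otherwise be made with the results in view.

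**What to change.** Before unblinding, amend SAP 3.7.2 and 7.2 as follows.

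1. Define the comparative endpoint on all randomised neonates: no antiseizure drug beyond the protocol phenobarbital doses within 24 hours of T0. Neonates who need no second dose are successes; those moved straight to another drug are not. State how withdrawals before 24 hours are scored.
2. Say that this is essentially the complement of the 24-hour alternative-therapy endpoint when that is counted cumulatively from T0, because Protocol 4.1.5 and 6.1.2 exclude maintenance phenobarbital from the Treatment Period. The two can be merged.
3. Report the percentage among second-dose recipients, and the time from second dose to alternative drug, as descriptive only, with no between-arm superiority inference.
4. Use the already listed time from first dose to alternative treatment, in all randomised neonates, as the comparative timing endpoint.

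The cost is a few lines of SAP text, with matching endpoint wording in the protocol if it is amended. Second doses and additional anticonvulsants are already recorded (Protocol 4.1, 4.1.3, 8.1.4), so there is no new data collection and no change to treatment or sample size.
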